APPENDIX 2. PARTIAL DATE CONVENTIONS

Imputed dates will not be presented in the listings. In the algorithms for date, 361-203 study med start date the date of first dose of study medication during double blind period.

ALGORITHM FOR ADVERSE EVENTS:

The concept of "date" below should also include time information whenever available.

START DATE	STOP DATE	ACTION
Known	Known	If start date < 361-203 study med start date, then pre-treatment events If start date >= 361-203 study med start date, then 361-203 AE
Known	Partial	If start date < 361-203 study med start date, then pre-treatment events If start date >= 361-203 study med start date, then 361-203 AE
Known	Missing	If start date < 361-203 study med start date, then pre-treatment events If start date >= 361-203 study med start date, then 361-203 AE
Partial, but known components show that it cannot be on or after 361-203 study med start date	Known	Pre-treatment events
Partial, but known components show that it cannot be on or after 361-203 study med start date	Partial	Pre-treatment events
Partial, but known components show that it cannot be on or after 361-203 study med start date	Missing	Pre-treatment events

Document:

\

Author:

Version Number:

Final 1.0

Version Date:

24FEB2020

Template No: CS_TP_BS016 Revision 4
Effective Date: 01Apr2016

Reference: CS_WI_BS005

START DATE	STOP DATE	ACTION
Partial	Partial	
Impute stop date as latest possible date (i.e. last day of month if day unknown or 31st December if day and month are unknown).
 
Then:
 
If stop date < 361-203 study med start date, then pre-treatment events
 
If stop date >= 361-203 study med start date, then 361-203 AE

Partial, could be on or after 361-203 study med start date	Known	
If stop date < 361-203 study med start date, then pre-treatment events
 
If stop date >= 361-203 study med start date, then 361-203 AE

Partial, could be on or after 361-203 study med start date	Partial	
Impute stop date as latest possible date (i.e. last day of month if day unknown or 31st December if day and month are unknown).
 
Then:
 
If stop date < 361-203 study med start date, then pre-treatment events
 
If stop date >= 361-203 study med start date, then 361-203 AE

Partial	Missing	Assumed 361-203 AE
Missing	Known	
If stop date < 361-203 study med start date, then pre-treatment events
 
If stop date >= 361-203 study med start date, then 361-203 AE

 Document:

\

Author:

Version Number:

Final 1.0

Version Date:

24FEB2020

 Template No: CS_TP_BS016 Revision 4
 Effective Date: 01Apr2016

Reference: CS_WI_BS005

START DATE	STOP DATE	ACTION
Missing	Partial	
Impute stop date as latest possible date (i.e. last day of month if day unknown or 31st December if day and month are unknown).
 
Then:
 
If stop date < 361-203 study med start date, then pre-treatment events
 
If stop date >= 361-203 study med start date, then 361-203 AE

Missing	Missing	Assumed 361-203 AE

Document:

\

Author:

Version Number:

Final 1.0

Version Date:

24FEB2020

Template No: CS_TP_BS016 Revision 4
Effective Date: 01Apr2016

Reference: CS_WI_BS005

ALGORITHM FOR PRIOR / CONCOMITANT / POST-TREATMENT MEDICATIONS:

The concept of "date" below should also include time information whenever available.

START DATE	STOP DATE	ACTION
Known	Known	If stop date < 361-203 study med start date, assign as prior. If stop date >= 361-203 study med start date and start date <= end of treatment, assign as concomitant. If stop date >= 361-203 study med start date and start date > end of treatment, assign as post treatment.
Known	Partial	Impute stop date as latest possible date: 
• If only day unknown, impute as the earlier of (last day of the month; date of the last study visit).• If month and day unknown, impute as the earlier of (31st December; date of the last study visit). Then: If stop date < 361-203 study med start date, assign as prior. If stop date >= 361-203 study med start date and start date <= end of treatment, assign as concomitant. If stop date >= 361-203 study med start date and start date > end of treatment, assign as post treatment.
Known	Missing	If stop date is missing could never be assumed a prior medication. If start date <= end of treatment, assign as concomitant. If start date > end of treatment, assign as post treatment.

Document:

\

Author:

Version Number:

Final 1.0

Version Date:

24FEB2020

Template No: CS_TP_BS016 Revision 4
Effective Date: 01Apr2016

Reference: CS_WI_BS005

START DATE	STOP DATE	ACTION
Partial	Known	
Impute start date as earliest possible date: CRF questions: 'Started prior to study?' = Yes; 'Started after last dose of study medication?' = No.
 
 • If only day unknown, impute as the later of (first day of the month; date of birth). • If month and day unknown, impute as the later of (1st January; date of birth). 
CRF questions: 'Started prior to study?' = No; 'Started after last dose of study medication?' = Yes.
 
 • If only day unknown, impute as the later of (first day of the month; end of treatment + 1). • If month and day unknown, impute as the later of (1st January; end of treatment + 1). 
CRF questions: 'Started prior to study?' = No; 'Started after last dose of study medication?' = No.
 
 • If only day unknown, impute as the later of (first day of the month; date of ICF). • If month and day unknown, impute as the later of (1st January; date of ICF). 
Then:
 
If stop date < 361-203 study med start date, assign as prior. If stop date >= 361-203 study med start date and start date <= end of treatment, assign as concomitant. If stop date >= 361-203 study med start date and start date > end of treatment, assign as post treatment.

Document:

\

Author:

Version Number:

Final 1.0

Version Date:

24FEB2020

Template No: CS_TP_BS016 Revision 4
Effective Date: 01Apr2016

Reference: CS_WI_BS005

START DATE	STOP DATE	ACTION
Partial	Partial	
Impute start date as earliest possible date: CRF questions: 'Started prior to study?' = Yes; 'Started after last dose of study medication?' = No.
 
 • If only day unknown, impute as the later of (first day of the month; date of birth). • If month and day unknown, impute as the later of (1st January; date of birth). 
CRF questions: 'Started prior to study?' = No; 'Started after last dose of study medication?' = Yes.
 
 • If only day unknown, impute as the later of (first day of the month; end of treatment + 1). • If month and day unknown, impute as the later of (1st January; end of treatment + 1). 
CRF questions: 'Started prior to study?' = No; 'Started after last dose of study medication?' = No.
 
 • If only day unknown, impute as the later of (first day of the month; date of ICF). • If month and day unknown, impute as the later of (1st January; date of ICF). 
Impute stop date as latest possible date:
 
 • If only day unknown, impute as the earlier of (last day of the month; date of the last study visit). • If month and day unknown, impute as the earlier of (31st December; date of the last study visit). 
Then:
 
If stop date < 361-203 study med start date, assign as prior.
 
If stop date >= 361-203 study med start date and start date <= end of treatment, assign as concomitant.
 
If stop date >= 361-203 study med start date and start date > end of treatment, assign as post treatment.

Document:

\

Author:

Version Number:

Final 1.0

Version Date:

24FEB2020

Template No: CS_TP_BS016 Revision 4
Effective Date: 01Apr2016

Reference: CS_WI_BS005

START DATE	STOP DATE	ACTION
Partial	Missing	
Impute start date as earliest possible date: CRF questions: 'Started prior to study?' = Yes; 'Started after last dose of study medication?' = No.
 
 • If only day unknown, impute as the later of (first day of the month; date of birth). • If month and day unknown, impute as the later of (1st January; date of birth). 
CRF questions: 'Started prior to study?' = No; 'Started after last dose of study medication?' = Yes.
 
 • If only day unknown, impute as the later of (first day of the month; end of treatment + 1). • If month and day unknown, impute as the later of (1st January; end of treatment + 1). 
CRF questions: 'Started prior to study?' = No; 'Started after last dose of study medication?' = No.
 
 • If only day unknown, impute as the later of (first day of the month; date of ICF). • If month and day unknown, impute as the later of (1st January; date of ICF). 
Then:
 
If stop date is missing could never be assumed a prior medication. If start date <= end of treatment, assign as concomitant. If start date > end of treatment, assign as post treatment.

Missing	Known	
If stop date < 361-203 study med start date, assign as prior. If stop date >= 361-203 study med start date and CRF question 'Started after last dose of study medication?' = No, assign as concomitant. If CRF question 'Started after last dose of study medication?' = Yes, assign as post treatment.

Document:

\

Author:

Version Number:

Final 1.0

Version Date:

24FEB2020

Template No: CS_TP_BS016 Revision 4
Effective Date: 01Apr2016

Reference: CS_WI_BS005

START DATE	STOP DATE	ACTION
Missing	Partial	
Impute stop date as latest possible date:
 
• If only day unknown, impute as the earlier of (last day of the month; date of the last study visit).• If month and day unknown, impute as the earlier of (31st December; date of the last study visit). 
Then:
 
If stop date < 361-203 study med start date, assign as prior.
 
If stop date >= 361-203 study med start date and CRF question 'Started after last dose of study medication?' = No, assign as concomitant.
 
If CRF question 'Started after last dose of study medication?' = Yes, assign as post treatment.

Missing	Missing	
If CRF question 'Started after last dose of study medication?' = No, assign as concomitant.
 
If CRF question 'Started after last dose of study medication?' = Yes, assign as post treatment.

Document:

\

Author:

Version Number:

Final 1.0

Version Date:

24FEB2020

Template No: CS_TP_BS016 Revision 4
Effective Date: 01Apr2016

Reference: CS_WI_BS005

PARTIAL DATE IMPUTATION RULES FOR INITIAL ONSET OF PARKINSON'S DISEASE OR PDP:

For subjects with partial onset dates of Parkinson's Disease or PDP, impute the onset date using the following rules:

- If only day unknown, impute as the earlier of: last day of the month, or date of ICF.
- If both month and day unknown, impute as the earlier of: 31st December of the year, or date of ICF.

Document:

\

Author:

Version Number:

Final 1.0

Version Date:

24FEB2020

Template No: CS_TP_BS016 Revision 4
Effective Date: 01Apr2016

Reference: CS_WI_BS005

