Electrocardiographic interval from the beginning of the QRS complex to the end of the T wave
QT interval corrected for heart rate
Rapid Eye Movement (REM) Sleep Behavioral Disorder
Rapid Eye Movement Sleep Behavior Disorder Questionnaire
Rapid eye movement
Respiration rate
Serious adverse event
Statistical analysis plan
Scale for Assessment of Positive Symptoms
Scale for Assessment of Positive Symptoms – Parkinson's Disease
Scales for Outcomes in Parkinson's Disease Sleep Scale – Daytime Sleepiness
Scales for Outcomes in Parkinson's Disease Sleep Scale – Nighttime Sleep Quality
System organ class
trace amine associated 1 receptors
United States, United States of America

Table 4: List of Abbreviations (Continued)

UPDRS	Unified Parkinson's Disease Rating scale
USP	United States Pharmacopeia
WBC	White blood cell
WHO-DD	World Health Organization Drug Dictionary
YOPD	Young onset Parkinson's disease

Table 5: Definition of Key Study Terms

Terms	Definition of terms
CRF	A printed, optical, or electronic document designed to record all of the protocol required information to report to the Sponsor for each study subject.
Screened Subject	Any subject who signed the study specific informed consent.
Screen Failures	Any subject who signed the study specific informed consent but either failed to meet study requirements during screening or met study requirements at screening but was not enrolled/randomized.
Study Drug (or Study medication) or Investigational Product	Term to cover investigational drug and placebo.
Treatment Period	The period of the study in which the double-blind study drug is administered.
Randomized Subject	Any subject who was randomized into the treatment period of the study and was assigned a randomization number.
Enrolled Subject	Any subject who was successfully screened and enrolled into the pre-randomization period of the study.
Randomization Failures	Any subject who was enrolled but not randomized.
Completed Subject	Any subject who completed the study by participating throughout the duration of the study, up to and including the last in-clinic visit.
Early Termination Subject	Any subject who was successfully screened and randomized into the treatment period of the study, but did not complete the study.
End of Treatment	The day that the subject receives protocol-defined last dose of the study drug. This may or may not include a taper period.
End of Study	The day that the subject completes the study per the study design.
1 Week	Defined as 7 days.

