10.5. Description of Study Periods

10.5.1. Description of Study Periods

The periods of the study, their duration, and subject status are provided below in Table 7.

Table 7: Description of Study Periods

Study Period	Visit Number	Study Day ^a (OL Study Day)	Inpatient/Outpatient
Screening	Visit 1	-14 to -1 (NA)	Outpatient
Double-blind Baseline	Visit 3	1 (NA)	Outpatient
Double-blind	Visit 4	8 (± 2 days) (NA)	Outpatient
Double-blind	Visit 5	15 (± 2 days) (NA)	Outpatient
Double-blind	Visit 6	29 (± 2 days) (NA)	Outpatient
Double-blind End/ Open-label baseline	Visit 7	43 (± 2 days) (OL Day 1)	Outpatient
Open-label Extension	Visit 8	50 (± 2 days) (OL Day 8)	Outpatient
Open-label Extension	Visit 9	57 (± 2 days) (OL Day 15)	Outpatient
Open-label Extension	Visit 10	64 (± 2 days) (OL Day 22)	Outpatient
Open-label Extension	Visit 11	71 (± 3 days) (OL Day 29)	Outpatient
Open-label Extension	Visit 12	99 (± 3 days) (OL Day 57)	Outpatient
Open-label Extension	Visit 13 / EOT / ET	127 (± 3 days) (OL Day 85)	Outpatient
Follow-up	Visit 14	7 days after last dose (± 2 days)	Outpatient

^a Study Day is based on Visit 3 (Day 1) and OL Day is based on Visit 7 (Study Day 43).

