6.8. STUDY MEDICATION

In this SAP, study medication refers to double-blind medication as well as open-label medication.

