12. MEDICATIONS

Medications will be presented for double-blind period and open label-period based on the double-blind safety population and open-label safety population respectively and coded using the WHO drug dictionary, Version 01JUN2016E or higher.

Whenever available, the time information should be accounted for in the derivation of prior, concomitant, and post-treatment medications. See APPENDIX 2 for the handling of partial dates for medications. In the case where it is not possible to define a medication as prior, concomitant, or post-treatment, the

Document:

\

Author:

Version Number:
Version Date:Final 1.0
24FEB2020Template No: CS_TP_BS016 Revision 4
Effective Date: 01Apr2016

Reference: CS_WI_BS005

medication will be classified by the worst case; i.e. concomitant.

For DB period,

- Prior medications are medications which stopped prior to the first dose of DB study medication.
- Summary of antipsychotic use prior to screening (total and %), by type: nuplazid, quetiapine (Seroquel), clozapine, other
- Concomitant medications are medications which started at the same time of or after the first dose of DB study medication and at the same time of or before the last dose of DB study medication; or started prior to and ended at the same time of or after the first dose of DB study medication; or started at the same time of or prior to the last dose of DB study medication and marked as ongoing.
- Post-treatment medications are medications which started after the last dose of DB study medication.

For OL period,

- Prior medications are medications which stopped prior to the first dose of OL study medication.
- Concomitant medications are medications which started at the same time of or after the first dose of OL study medication and at the same time of or before the last dose of OL study medication; or started prior to and ended at the same time of or after the first dose of OL study medication; or started at the same time of or prior to the last dose of OL study medication and marked as ongoing.
- Post-treatment medications are medications which started after the last dose of OL study medication.

Prior and concomitant medication use will be summarized by Anatomical Therapeutic Chemical (ATC) Level 3 classification and preferred name using frequencies and percentages. Prior, concomitant, and post-treatment medications will be provided in data listings.

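### SAP Appendix 2 classifies medications with one treatment window for both periods, which conflicts with the period-specific definitions in SAP Section 12

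*SAP*

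**What the plan says.** SAP Section 12 presents medications by period and gives each period its own definitions. For the DB outputs, "Post-treatment medications are medications which started after the last dose of DB study medication". For the OL outputs, "Prior medications are medications which stopped prior to the first dose of OL study medication". Protocol Section 15.3.6.6 likewise has a separate paragraph that classifies extension medications against the first and last extension dose.

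Section 12 refers to Appendix 2 for partial dates. It adds that a medication that cannot be classified is treated as concomitant, as the worst case.

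Appendix 2 has one medication algorithm. Its start anchor is fixed in the opening paragraph: "361-203 study med start date the date of first dose of study medication during double blind period". The row for a fully known start and stop date reads "If stop date >= 361-203 study med start date and start date <= end of treatment, assign as concomitant". The rows in which only one or both dates are partial impute a date and then apply the same test. No row refers to the first OL dose or the last DB dose, and there is no OL version.

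The SAP does not define end of treatment. Protocol Table 5 defines it as "The day that the subject receives protocol-defined last dose of the study drug", and Protocol Table 7 labels the last OL visit "Visit 13 / EOT / ET". However, Table 5 also defines Treatment Period as "The period of the study in which the double-blind study drug is administered".

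**The concern.** One window cannot serve two periods that have different first and last doses. A programmer who follows Appendix 2 will get a different answer from one who follows Section 12, and this includes records with complete dates. For partial or missing dates Section 12 hands over to Appendix 2, so apart from the fallback to concomitant there is no period-specific rule to use.

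At stake is whether each period's medication table shows what subjects took in that period. After Day 43 all continuing subjects receive SEP-363856, so a drug first taken in the extension does not belong in the randomized-arm columns of the DB table. Nor does a drug already stopped before the extension belong among the OL concomitant medications.

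**Working it through.** There is no planned figure to reproduce. The check applies both rules to the same records.

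**Inputs.** For a subject dosed on schedule, the DB doses run from Day 1 to Day 42 and the OL doses from Day 43 to Day 126 (Protocol Table 3, footnotes a, c and h).

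**Rules.** Write F and L for a period's first and last dose, and E for end of treatment.
- Section 12: prior if stop < F; concomitant if stop ≥ F and start ≤ L; post-treatment if start > L. DB uses F = 1, L = 42. OL uses F = 43, L = 126.
- Appendix 2: prior if stop < 1; concomitant if stop ≥ 1 and start ≤ E; post-treatment if stop ≥ 1 and start > E. Here E = 126 (overall last dose) or E = 42 (last DB dose).

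**Results.**

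| Drug taken (days) | Section 12, DB | Section 12, OL | Appendix 2, E = 126 | Appendix 2, E = 42 |
|---|---|---|---|---|
| −20 to −5 | prior | prior | prior | prior |
| −20 to 20 | concomitant | prior | concomitant | concomitant |
| 10 to 20 | concomitant | prior | concomitant | concomitant |
| 30 to 60 | concomitant | concomitant | concomitant | concomitant |
| 60 to 80 | post | concomitant | concomitant | post |
| −20 to 130 | concomitant | concomitant | concomitant | concomitant |
| 128 to 130 | post | post | post | post |

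Four intervals agree with Section 12 for both periods. Three do not:
- Days −20 to 20 and Days 10 to 20 are wrong for OL under both values of E. Each stop date satisfies 20 ≥ 1, so Appendix 2 cannot return prior. Section 12 gives prior because 20 < 43.
- Days 60 to 80 is wrong for DB if E = 126 (60 ≤ 126, but Section 12 has 60 > 42). It is wrong for OL if E = 42 (60 > 42, but Section 12 has 60 ≤ 126).

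With F and L of each period substituted for the Appendix 2 anchors, all seven intervals match Section 12 in both periods.

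**Missing dates.** Take a missing start, a stop on Day 20, and a CRF answer that the drug was not started after the last dose. Section 12 needs only the stop date to call this prior for OL (20 < 43). The Appendix 2 row calls it concomitant. When both dates are missing, that CRF item alone decides between concomitant and post-treatment. It cannot separate the periods, because "In this SAP, study medication refers to double-blind medication as well as open-label medication".

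**The case against.** The strongest reply is that Section 12 holds the operative definitions and classifies every complete-date example above correctly. Appendix 2 is titled, and cited, as a partial-date convention. SAP Section 13.1 takes DB and OL dose dates from separate eCRF forms, so a programmer has what is needed to apply Section 12. This stands to the extent that the documents do not settle on a miscount: a reader might infer that the DB table will contain extension drugs, but the text shows only two rules in conflict. It does not remove the conflict, because Appendix 2 restates the classification for known dates with different anchors and is the rule Section 12 uses for partial ones.

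Second, reading end of treatment as the overall last dose is an inference. The Table 5 definition, the Visit 13 label and SAP Section 6.8 favour it; the Table 5 entry for Treatment Period points the other way. This stands for the DB consequence, which disappears if the term means the last DB dose. The error then moves to the OL table, and the error for drugs stopped in the DB period remains in either case.

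Third, Section 12's fallback to concomitant covers records that cannot be classified. It does give them an assignment, but it does not say in which period's table.

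Fourth, a reader might conclude that the comparison of rescue use is no longer a double-blind one. The documents do not support that. SAP Section 16 separately plans descriptive statistics for anxiolytic or hypnotic use since the last visit, and SAP Section 9 handles disallowed drugs through deviation review by period. The DB analyses also have their own database lock (SAP Section 4), and the plan does not say which extension records would be present at that lock.

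Fifth, it is tempting to size the problem by the share of treatment days that are open-label. That needs a constant rate of new drug starts, completion of the extension and the overall reading. Nothing in the documents supports the first of these, and Protocol Section 10.3.1 restricts regimen changes and new psychotropic drugs.

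**Conclusion.** The conflict is real and holds under either meaning of end of treatment: no single window reproduces Section 12 for both periods. Applied as written, Appendix 2 makes a drug stopped during the DB period concomitant instead of prior in the OL table. It also puts a drug started in the OL period in the wrong class in one table, and which table depends on the undefined term.

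The three discordant intervals out of seven show which kinds of record are affected. They are not an estimate of how many subjects would change class; the documents give no basis for one. The example days assume dosing on schedule and entry into the extension. The effect is confined to descriptive medication tables and listings: Section 12 plans frequencies and percentages with no test, and nothing in the plan feeds this classification into an efficacy endpoint. It should be corrected before programming, as an inconsistency within the SAP rather than a threat to the trial's conclusions.

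**What to change.** In Appendix 2, run the medication algorithm once per period. For the DB outputs, replace the study medication start date and end of treatment with the first and last DB dose; for the OL outputs, use the first and last OL dose. Make the same substitution wherever end of treatment appears in the imputation steps. State how the CRF item on starting after the last dose is used for each period, and that the fallback to concomitant applies within the period being tabulated. Add a sentence that Section 12 governs when both dates are complete.

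The cost is a few sentences in the SAP and a second pass of the same program. Both sets of dose dates are already collected (SAP Section 13.1), so no new data are needed.
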